8. OUTPUT PRESENTATIONS

Appendix 1 shows conventions for presentation of data in outputs.

The templates provided with this SAP describe the presentations for this study and therefore the format and content of the summary tables, figures, and listings to be provided by IQVIA Biostatistics.

Document:	\\ieedc-vnasc01\Biosdata\Menarini\NebAml\ZZA67778\Biostatistics\Documentation\SAP\SAP_Menarini_MEIN21AmNe-Hyp001_Final_V1.0		
Author:	[name]	Version Number:	Final V1.0
		Version Date:	11Nov2022
Template No.:	CS_TP_BS016 Revision 7	Reference:	CS_WI_BS005
Effective Date:	01Nov2021		

9. DISPOSITION AND WITHDRAWALS

All patients who provide informed consent will be accounted for in this study.

9.1. Disposition

Patient disposition and withdrawals will be presented for All Patients.

Number of patients in each population, including reasons for exclusion, will be presented for ENR population.

A listing of inclusion and exclusion criteria will be presented for the Screen Failures.

9.2. Protocol Deviations

All protocol deviations (PD) will be discussed and reviewed on a case-by-case basis before the DBL at the data review meeting. All PDs reviewed by Sponsor will be documented.

Individual PDs will be presented in a data listing. The number and percentage of patients with Critical/Major PDs will be summarized by deviation on ENR population. PD summary will be classified into “Monotherapy” and “Combination Therapy” based on the incidence date of PD. Additional Critical, Major and Minor PDs may be identified during data review and will be agreed upon with the Sponsor and reflected in the Table and Listing as appropriate.

All PDs will be recorded and classified in Clinical Trial Management System (CTMS) before the Data review Meeting.

9.3. COVID-19 IMPACT

The impact of COVID-19 on study related procedures are collected on ‘COVID-19 Impact Log’ in eCRF. Impact information which includes Assessment/Procedure Impacted, Type of Impact, and Reason for Impact will be presented in a summary table and a data listing for ENR population.

10. DEMOGRAPHIC AND OTHER BASELINE CHARACTERISTICS

Demographic data and other baseline characteristics will be presented for the ENR population.

No statistical testing will be carried out for demographic or other baseline characteristics.

Document: \\eedc-vnasc01\Biosdata\Menarini\NebAml\ZZA67778\Biostatistics\Documentation\SAP\SAP_Menarini_MEIN21AmNe-Hyp001_Final_V1.0

Author: [name]

Version Number:

Final V1.0

Version Date:

11Nov2022

Template No.: CS_TP_BS016 Revision 7

Reference: CS_WI_BS005

Effective Date: 01Nov2021

The following demographic and other baseline characteristics will be reported for this study:

- Age (years)
- Age Category (<40 Years, ≥40 Years)
- Sex
- Childbearing potential
- Race
- Hypertensive Medication status at Screening (Visit 1)
 - NEB 5mg or AML 5 mg
 - Other BBs or CCBs
- Weight (kg)
- Height (cm)
- BMI (kg/m²)
- Presence of Type 2 diabetes mellitus at Screening (Yes/ No)
- Hypertension grade at Screening
- Presence of Hypercholesterolemia at Screening (with Hypercholesterolemia/ without Hypercholesterolemia)
- Mean sitting DBP at Screening (mmHg)
- Mean sitting SBP at Screening (mmHg)

10.1. Derivations

- $BMI (kg/m^2) = \text{weight (kg)} / \text{height (m)}^2$

11. MEDICAL HISTORY AND PROCEDURES

Medical History information will be presented by Monotherapy for the ENR Population.

- Medical History data captured on eCRF form “Medical History/Concurrent Diseases” will be coded using Medical Dictionary for Regulatory Activities (MedDRA, Version 24.1 or latest) dictionary
 - Medical History conditions are defined as those conditions which stopped prior to or at Screening.
 - Presented by SOC and PT.

A separate listing for Medical Procedures information collected on eCRF form “Medical

Document: \\weedc-vnasc01\Biosdata\Menarini\NebAm\ZZA67778\Biostatistics\Documentation\SAP\SAP_Menarini_MEIN21AmNe-Hyp001_Final_V1.0

Author: [name]

Version Number:

Final V1.0

Version Date:

11Nov2022

Template No.: CS_TP_BS016 Revision 7

Reference: CS_WI_BS005

Effective Date: 01Nov2021

Procedures” will be presented by Monotherapy for the ENR Population.

12. CONCURRENT DISEASE

Concurrent Disease will be presented for the SAF population.

- Concurrent Diseases will be coded using Medical Dictionary for Regulatory Activities (MedDRA, Version 24.1) dictionary
 - Concurrent Diseases are conditions started prior to or at Screening and are ongoing at the date of Screening.
 - Presented by SOC and PT.
 - Concurrent Diseases conditions are defined as those conditions recorded in the eCRF form “Medical History/Concurrent Diseases”.

13. PRIOR AND CONCOMITANT MEDICATIONS

Medications, recorded in the eCRF form “Prior and Concomitant Medications”, will be presented for the SAF population and coded using WHO Drug dictionary Version 01SEP2020 or latest. Frequency tabulations will be presented for prior and concomitant medications by primary therapeutic subgroup (3rd level ATC code) and preferred name for Monotherapy and Combination Therapy.

See Appendix 2 for handling of partial dates for medications, in the case where it is not possible to define a medication as prior, concomitant, or post treatment, the medication will be classified by the worst case, i.e., concomitant.

- ‘Prior’ medications are medications which started and stopped prior to the first dose of monotherapy.
- ‘Concomitant’ medications are medications which:
 - started prior to, on or after the first dose of study medication,
 - AND ended on or after the date of first dose of study medication or were ongoing at the end of the study.
 - Concomitant medications that are started prior to the first dose of Combination Therapy will be summarized under “Monotherapy”.
 - Concomitant medications that are started after the first dose of Combination Therapy will be summarized under “Combination Therapy”.

Document: \\eedc-vnasc01\Biosdata\Menarini\NebAml\ZZA67778\Biostatistics\Documentation\SAP\SAP_Menarini_MEIN21AmNe-Hyp001_Final_V1.0

Author: [name]

Version Number:

Final V1.0

Version Date:

11Nov2022

Template No.: CS_TP_BS016 Revision 7

Reference: CS_WI_BS005

Effective Date: 01Nov2021

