- c. Patients on NEB 5 mg or AML 5 mg will continue the same therapy for 4 weeks (run-in period). Patients on any other BBs will be assigned to monotherapy with NEB 5 mg and the patients on other CCBs (except AML 10 mg) will be assigned to monotherapy with AML 5 mg. The allowed CCBs are: felodipine, lacidipine, lacidipine, nicardipine, nicardipine, nimodipine, and nisoldipine).
- d. Only patients with controlled BP at Visit 3 will receive NEB/AML 5/5 mg for next 4 weeks.
- e. Only patients with uncontrolled BP at Visit 3 will receive NEB/AML 5/10 mg for next 4 weeks.
- f. All concomitant medications ongoing at the time of the consent and any surgery/procedures should be reported.
- g. Pregnancy test (urine): only for females of childbearing potential.
- h. Vital signs will include body temperature, respiratory rate, and pulse rate.
- i. To ensure patient safety, the patients will be contacted over a phone call within 24 hours, in case of any abnormality and clinically relevant laboratory test according to the Investigator's judgment at any visit.

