## 7.5 Concomitant Therapy(ies)

Any medication that the patient was receiving at the time of enrolment, and the other regular or occasional use of any concomitant medication during the study will be recorded in the source documents and in the eCRF. Whenever possible, without jeopardizing the patients care, study patients should remain on the same concomitant medication at a stable dose throughout the study. In order to facilitate recording of medication history, patients will be asked to bring their medication, preferably in their original packaging.

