### 12.5 Statistical Analysis

### 12.5.1 Descriptive statistics

Patient disposition, demographics and baseline characteristics will be summarized for monotherapy and combination therapy. Medical history will be summarized only for monotherapy. Prior and concomitant medications will be summarized for combination therapy (NEB + AML).

Continuous variables will be summarized using the number of non-missing observations, mean, SD, minimum, median, and maximum values. Categorical variables will be presented with the number of non-missing observations and column percentages (n, %).

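### SAP 13 places concomitant medications in a period by start date alone, so the Combination Therapy column shows only new starts and omits medication already in use at the first combination dose

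*SAP*

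**What the plan says.** SAP 13 promises frequency tables of prior and concomitant medications by ATC group and preferred name, for Monotherapy and for Combination Therapy, in the Safety population. A medication is prior if it began and finished before the first monotherapy dose. It is concomitant if it began at any time "AND ended on or after the date of first dose of study medication or were ongoing at the end of the study".

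Two further lines assign the column. The first reads "Concomitant medications that are started prior to the first dose of Combination Therapy will be summarized under" Monotherapy. The second reads "Concomitant medications that are started after the first dose of Combination Therapy will be summarized under" Combination Therapy. Neither refers to the stop date.

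Three places in the protocol bear on this:

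- Section 12.5.1, on the summary required: "Prior and concomitant medications will be summarized for combination therapy (NEB + AML").
- Section 7.5, on the expected pattern of use: as far as clinical care allows, "study patients should remain on the same concomitant medication at a stable dose throughout the study".
- Section 2.2, flow chart footnote f, on what is recorded: "All concomitant medications ongoing at the time of the consent and any surgery/procedures should be reported".

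**The concern.** A medication is taken over an interval, but the rule treats it as an event with an onset. A drug begun before Visit 2 and taken through Week 8 is in use throughout the assessment period, yet it is tabulated only under the run-in treatment.

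The protocol encourages stable co-medication and collects whatever is ongoing at Visit 1, about four weeks before the first combination dose. The column meant to describe treatment alongside the combination thus leaves out the kind of medication that the protocol expects patients to be on.

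At stake is a plain description of co-treatment in an uncontrolled before-and-after study. A reader will want it beside the change in DBP and beside the adverse events that SAP 18.1 reports under Combination Therapy. Read at face value, the column would suggest less co-medication than patients were taking.

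**Working it through.** The documents state no figure to reproduce, so the check follows the rule through the text.

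**Step 1: what makes a medication concomitant.** The stop date is used here and only here. I read the first dose of study medication as the first dose of either kind, which fits SAP 5.3 and the SAP 13 definition of a prior medication.

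**Step 2: what decides the column.** Only the start date relative to the first combination dose. The two conditions exclude each other, and nothing says that a carried-over drug is also counted under Combination Therapy.

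**Step 3: hypothetical medications under the rule.**

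| Medication | Column under SAP 13 | Column(s) by period of use |
|---|---|---|
| A: started before consent, continued to Week 8 | Monotherapy | Both |
| B: started and stopped within run-in | Monotherapy | Monotherapy |
| C: started in run-in, continued to Week 8 | Monotherapy | Both |
| D: started after the first combination dose | Combination | Combination |
| E: started on the day of the first combination dose | Not stated in SAP 13 | Combination |

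A and C are missing from the Combination column. If the first dose of study medication in Step 1 is instead read as the first combination dose, B falls outside the concomitant definition, but A and C are placed as before.

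**Step 4: does another section change this?** SAP Appendix 2 sorts medications into prior, concomitant and post-treatment; it does not assign columns. SAP 3.3 lists five changes from the protocol, and this is not one of them.

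**Step 5: can the Monotherapy column stand in?** No. It pools A, B and C, so continued drugs cannot be told from stopped ones. It also covers Safety-population patients who were withdrawn at Visit 2 (Protocol 5) and never took the combination.

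**Step 6: size.** Among medications in use at the first combination dose and continued, the share omitted from the Combination column is 100%, by rule. As a share of all medication taken in weeks 0 to 8 it is

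share omitted = a / (a + n),

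where a is the number of carried-over medications per patient and n the number of new starts per patient. The documents give neither. Purely as an assumption, take a between 1 and 2 and n between 0.05 and 0.30:

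- lowest: 1 / (1 + 0.30) = 0.77
- highest: 2 / (2 + 0.05) = 0.98

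This shows how the share behaves. It does not estimate this trial.

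**The case against.** **The information is moved, not lost.** Carried-over drugs appear in the adjacent column, and the remark in Appendix 2 about dates in listings suggests that dated medication listings will exist. This stands in part: a listing would let someone rebuild the picture, but the table would not show it (Step 5).

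**Onset-based assignment is the SAP's convention.** Adverse events (SAP 18.1) and protocol deviations (SAP 9.2) are also assigned by date of onset or incidence, and Protocol 12.5.1 does not prescribe counting by overlap. That is so, but a summary for combination therapy that excludes drugs taken with the combination does not serve its stated purpose. The output templates are not among the documents. They might display carried-over drugs differently, but the SAP text does not provide for it.

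**Stronger readings.** A reader might infer more than the documents support:

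- *Nearly all co-medication is omitted.* There are no counts, and the stable-dose instruction in Protocol 7.5 is qualified by the needs of patient care.
- *Every chronic drug will show 0% under Combination Therapy.* This is true only of carried-over use. A row is an ATC group or preferred name, and it still counts patients who newly start that drug.
- *Prohibited blood-pressure drugs would go unseen, so the DBP change could not be attributed to study treatment.* Such drugs are barred by Protocol 7.6, and their use can lead to withdrawal under Protocol 10. Deviations are reviewed case by case and listed individually (SAP 9.2). Major ones that could affect the primary analysis remove the patient from the PP population (SAP 5.4), on which that analysis is repeated (SAP 16.1.5). A frequency table has no within-patient link to DBP in any case, and a drug stable across Visit 2 confounds a within-patient change less than a new start, which the column does show.
- *Same-day starts are unassigned.* SAP 6.1 sets the reference start date at the first combination dose, and SAP 6.2 treats medications beginning then as post-baseline. What remains is a mismatch of wording in SAP 13.

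**Conclusion.** The point holds as a defect in a descriptive table. By its plain wording, SAP 13 leaves every medication that was ongoing at the first combination dose and then continued out of the Combination Therapy column. The column therefore understates co-medication in weeks 0 to 8, falls short of what Protocol 12.5.1 asks for, and departs from it without an entry in SAP 3.3.

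The size is known only in part: the omission is total for carried-over use and unquantified as a share of all use. No endpoint, test, analysis population or sample size changes. Neither the paired analysis of DBP nor the repeated-measures model uses co-medication.

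The conclusion assumes that the output templates follow the SAP text. It is a minor point, worth correcting because the stated rule gives a misleading column.

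**What to change.** Replace the two column rules in SAP 13 with one that counts a medication in every period its start-to-stop interval overlaps:

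- **Monotherapy:** taken at any time between the first run-in dose and the first combination dose.
- **Combination Therapy:** ongoing at the first combination dose, or started on or after that date. This also brings same-day starts into line with SAP 6.2.

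State that the Combination column's denominator is patients who received at least one combination dose. SAP 7 bases percentages on the relevant population and treatment arm, which may already intend this, but SAP 13 names only the Safety population.

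The cost is about one sentence of SAP text and a small programming change. The start and stop dates are already needed for Appendix 2. The drawback is that a medication can appear in both columns, so they no longer add up to a total; a table footnote should say so.

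If the sponsor prefers to keep the start-date rule, SAP 3.3 should list it as a departure from Protocol 12.5.1, and the column should be labelled as showing new starts only.

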14. STUDY MEDICATION EXPOSURE

Exposure to study medication for both Monotherapy and Combination therapy in days will be presented for the SAF population.

The date of first study medication administration will be taken from the eCRF “Exposure” form.

The date of last study medication will be taken from the eCRF “End of Study Treatment” form.

Interruptions, compliance, and dose changes are not taken into account for duration of exposure.

14.1. Derivations

Duration of exposure (days) = date of last study medication administration – date of first study medication administration + 1.

15. STUDY MEDICATION COMPLIANCE

Compliance to study medication (i.e., monotherapy and/or combination therapy) will be presented for the mITT and SAF populations.

A table consisting of summary statistics for percent compliance along with the number and percent of patients with compliance in each of the following groups:

- Low: percentage of compliance <80%
- Normal: percentage of compliance =>80% - <=120%
- High: percentage of compliance >120%

on SAF population for Monotherapy, and mITT as well as SAF populations for Combination Therapy. By visit (Visit2 and Visit 3) and overall compliance will be produced for Combination Therapy.

A listing of drug accountability will be presented on mITT and SAF populations by phase to account for all drug distributed to each patient, including the box number, total number tablets dispensed, returned, consumed, lost (if any), percentage compliance and compliant (yes/no).

15.1. Derivations

Monotherapy and Combination Therapy compliance with study drug based on the drug accountability data will be calculated as the number of tablets taken x 100 / expected number of

Document: \\needc-vnasc01\Biosdata\Menarini\NebAml\ZZA67778\Biostatistics\Documentation\SAP\SAP_Menarini_MEIN21AmNe-Hyp001_Final_V1.0

Author: [name]

Version Number:

Final V1.0

Version Date:

11Nov2022

Template No.: CS_TP_BS016 Revision 7

Reference: CS_WI_BS005

Effective Date: 01Nov2021

tablets which should have been taken expressed as a percentage.

For Monotherapy, the expected number of tablets to be taken = (Treatment End Date – Treatment Start Date) + 1.

For Combination Therapy, the expected number of tablets to be taken = 2 * ((Treatment End Date – Treatment Start Date) + 1).

For patients who permanently stop the study medication (i.e., monotherapy and/or combination therapy), the expected number of tablets will be calculated up-to the date of study withdrawal.

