## 7 STUDY TREATMENT

The following study treatment are administered during:

- Run-in period (Visit 1 to Visit 2): NEB 5 mg tablets or AML 5 mg tablets in patients who were already receiving NEB 5 mg or AML 5 mg or who were on any other BBs or CCBsc, respectively prior to enrolment into the study.
- Assessment period (Visit 2 to Visit 3): Extemporaneous combination of NEB 5 mg and AML 5 mg in patients with uncontrolled BP at Visit 2.
- Assessment period (Visit 3 to Visit 4): Extemporaneous combination of NEB 5 mg and AML 5 mg in patients with controlled BP at Visit 3 and extemporaneous combination of NEB 5 mg and AML 10 mg in patients with uncontrolled BP (sitting SBP/DBP >130/80 mmHg, who tolerated the treatment and whose adherence to the therapies ranges from 80% to 120%) at Visit 2.

Details on the study design is provided in Section 5.

Further details on study treatment is provided below in Table 7.1.

MENARINI	Corp	porate Medical Departm	ent
	Protocol Template		
Identification Number	Version Number	State	Effective date
FORM-000050125	2.0, CURRENT	Effective	08 Jan, 2021

Study Code: MEIN/21/AmNe-Hyp/001

Table 7.1Study Treatment Details	
----------------------------------	--

Study Treatment Name:	Nebivolol Marketing Authorisation Holder : A. Menarini Industrie Farmaceutiche Riunite srl, [name]	Amlodipine Besylate Marketing Authorisation Holder: EG S.p.A. [name] (MAH)
Dosage Formulation:	Tablet	Tablet
Unit Dose Strength(s)/Dosage	5 mg once daily	5 mg/10 mg once daily
Level(s):		
Route of Administration:	Oral	Oral
Dosing Instructions*:	1 tablet of study medication will be administered with a glass of water once daily	1 tablet of study medication will be administered with a glass of water once daily
Packaging and Labelling:	Study medication will be provided in a polyvinyl chloride (PVC)/Aluminum blister	Study medication will be provided in a Aluminum/PVC/polyethylene (PE)/ polyvinylidene chloride (PVDC) blister

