### 7.4 Study Product Compliance

Compliance with study treatment will be assessed at Visit 2 for monotherapy and Visit 3 and Visit 4 for the combination therapy. The PI must instruct patients to return the medications at each visit. The amount of study medication taken by the patient will be derived by counting the number of tablets in the blister returned and will be recorded in the source document and in the electronic case report form (eCRF).

Adherence to treatment will be measured through treatment compliance which will be calculated by using the below formula:

 $\frac{\textit{number of doses taken during the study}}{\textit{number of doses to be taken during the study}} \times 100$ 

MENARINI	Corporate Medical Department		ent
	]	Protocol Template	
Identification Number	Version Number	State	Effective date
FORM-000050125	2.0, CURRENT	Effective	08 Jan, 2021

Study Code: MEIN/21/AmNe-Hyp/001

A patient who has taken at least 80% and no more than 120% of the required study medication intake since the last visit will be considered as compliant.

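### Combination compliance pools nebivolol and amlodipine tablets, so a patient can be classed Normal while missing up to about 40% of one drug, provided the other is taken in full

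*SAP*

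**What the plan says.** SAP 15.1 uses one ratio for both treatment phases: compliance is "calculated as the number of tablets taken x 100 / expected number of" tablets. For the run-in the denominator counts one tablet per day: "For Monotherapy, the expected number of tablets to be taken = (Treatment End Date – Treatment Start Date) + 1". For the assessment period it counts two per day: "For Combination Therapy, the expected number of tablets to be taken = 2" multiplied by the days on treatment. The numerator is not split by drug.

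SAP 15 sorts the result into three classes, the middle one being "Normal: percentage of compliance =>80% - <=120" (in percent). It plans summary statistics and class counts by visit and overall for the combination, and an accountability listing that carries box numbers, tablet counts, the compliance percentage and a compliant yes/no flag. No summary by drug is planned.

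Protocol 7.4 applies the same band; under its rule, intake of "at least 80% and no more than 120% of the required study medication intake since the last visit will be considered as compliant". It sets no condition for each drug.

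On dosing, Table 7.1 in Protocol 7 states for each drug: "1 tablet of study medication will be administered with a glass of water once daily". Protocol 7.1 supplies the two drugs in separate boxes of 42 tablets each, dispensed together at Visits 2 and 3. Adherence at Visits 2, 3 and 4 is a listed secondary endpoint (Protocol 4).

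**The concern.** The combination is two tablets, not one, so intake of the two drugs can diverge in a way that a fixed-dose tablet would rule out. A pooled count averages the two and hides the divergence. The band applied to that average then answers whether enough tablets were taken in total. It does not answer whether both drugs were taken.

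That second question is why the endpoint exists: Protocol 4 justifies it as a help in judging the efficacy and tolerability of the combination. It also bears on the secondary comparison of NEB/AML 5/10 mg with 5/5 mg, where only the amlodipine dose differs and amlodipine intake is never summarised by itself. At stake is whether the reported share of compliant patients can be read as the share who took both components as planned.

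**Working it through.** The plan states no figure to reproduce, so the SAP formula is applied directly.

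**Inputs**
- One tablet of each drug per day (Protocol 7, Table 7.1).
- Interval between combination visits: 4 weeks ±2 days, i.e. 26 to 30 days (Protocol 5).
- Normal band: 80% to 120%, both ends included (SAP 15).
- Supply: 42 tablets of each drug per dispensing (Protocol 7.1).

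**Formula.** Let a and b be the tablets of each drug taken, divided by the days in the interval. Then

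pooled compliance = (a × days + b × days) / (2 × days) = (a + b) / 2.

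The pooled value is exactly the mean of the two component values. The lower limit of the band requires only (a + b)/2 ≥ 0.80, that is b ≥ 1.60 − a.

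**How much of one drug can be missed, given intake of the other**

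| Other drug (a) | Lowest b still Normal | Tolerated gap |
|---|---|---|
| 100% | 60% | 40% |
| 95% | 65% | 35% |
| 90% | 70% | 30% |
| 80% | 80% | 20% |

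**Whole tablets, other drug taken in full**

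| Days | Missed of one drug | Pooled | Class | That drug alone |
|---|---|---|---|---|
| 26 | 10 | 42/52 = 80.8% | Normal | 16/26 = 61.5% |
| 28 | 11 | 45/56 = 80.4% | Normal | 17/28 = 60.7% |
| 28 | 12 | 44/56 = 78.6% | Low | 16/28 = 57.1% |
| 30 | 12 | 48/60 = 80.0% | Normal | 18/30 = 60.0% |
| 56 | 22 | 90/112 = 80.4% | Normal | 34/56 = 60.7% |
| 56 | 23 | 89/112 = 79.5% | Low | 33/56 = 58.9% |

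So 40% is a limit. It is reached exactly at 30 days; at 28 days the most that passes is 11/28 = 39.3%.

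**Upper end.** One drug at 140% and the other at 100% gives (1.40 + 1.00)/2 = 120%, still Normal.

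**Theoretical bounds.** If a whole 42-tablet box counts as taken in 28 days, that drug reads 42/28 = 150%. Then 42 + 14 = 56 gives 56/56 = 100% with the other drug at 14/28 = 50%, and 42 + 3 = 45 gives 45/56 = 80.4% with the other at 3/28 = 10.7%. Apparent over-intake need not be real: intake is derived from tablets returned (Protocol 7.4), so an unreturned 14-tablet blister that is not recorded as lost would read as taken. That route is an inference from the counting method; the documents report no such case.

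**With the band applied per drug.** In the 28-day example the components are 28/28 = 100% (Normal) and 17/28 = 60.7% (Low). The shortfall becomes visible.

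**The case against.** The strongest reply is that little depends on this.

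- Patients are told to take both tablets together once a day (Protocol 7.1), so missed doses will often be missed for both drugs, and the pooled ratio then describes each drug well. The documents do not say how often the two diverge. This limits the likely size and stands.
- With one tablet of each per day the pooled percentage is a true mean of the two components. The summary statistics in SAP 15 are therefore valid as average adherence; only the class and the yes/no flag can mislead. This also stands.
- The accountability listing carries box numbers, and each drug has its own box, so an imbalance may be seen patient by patient. That is partial help: the SAP does not say that rows are per drug, and a listing does not correct the summary table.
- Protocol 7.4 sets no condition per drug, so requiring both components in the band is stricter than the protocol. That is true. It is a reason to declare the change, and the separate percentages are useful even to someone who would keep the pooled class.

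A reader might infer more: that anyone who skips 40% of one drug passes, that Normal patients may have been in effect on monotherapy for much of the period, or that the efficacy results are compromised. The documents do not support these. The first omits the condition that the other drug is taken in full. The second needs the over-intake cases above; without over-intake a Normal patient can miss one drug on at most 11 of 28 days. On the third, the Visit 2 entry check counts a single drug, the mITT definition (SAP 5.2) does not use compliance, and so the primary analysis does not depend on this ratio. The per-protocol population (SAP 5.4) rests on major deviations reviewed case by case (SAP 9.2), and neither document lists a pooled-compliance cut-off among them, so an effect there is not shown.

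**Conclusion.** The point holds for the compliance classification in the combination period. As SAP 15.1 is written, a patient can be counted as Normal and flagged compliant while one of the two drugs is well below 80%: down to about 60% if the other is taken in full, and down to 70% if the other is at 90%. Gaps beyond 40% are bounds that need apparent over-intake of one drug and should not be read as expected cases.

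This rests on one tablet of each drug per day, intervals of about 28 days, and the numerator including tablets of both drugs, which is the reading consistent with a denominator of two per day. The share of patients who would change class cannot be estimated from the documents. The consequence is confined to a descriptive secondary endpoint. It should be corrected because the stated rule can give the wrong class for the purpose the protocol assigns to it, and because correction is cheap.

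**What to change.** In SAP 15 and 15.1:

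1. Compute compliance separately for nebivolol and amlodipine in each dispensing interval (Visit 2 to 3 and Visit 3 to 4) and overall, as tablets of that drug taken divided by days, with the existing 80% to 120% band.
2. Tabulate the percentage and the Low/Normal/High class for each drug.
3. Class a patient as Normal for the combination, and flag the patient as compliant, only if both drugs are in the band.
4. Keep the pooled percentage as an additional row, so that the ratio now defined is still reported.
5. Record the change in SAP 3.3, since Protocol 7.4 sets no condition per drug.

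The drugs are boxed separately and returned tablets are already counted, so this should need minor programming and no new study procedure. The price is a compliance figure that may be slightly less favourable.
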